### **9.3 Clinical Laboratory Data**

Clinical laboratory data obtained from central measurements will be used for analyses. For clinical laboratory test parameters other than qualitative urinalysis, measured values and changes from baseline at each time point and at the time of final IMP administration will be summarized using descriptive statistics. For qualitative urinalysis parameters, shift tables will be prepared at each time point and at the time of final IMP administration compared with baseline. In addition, measured values of clinical laboratory test parameters other than qualitative urinalysis will be categorized as below, within, or above the normal range, and shift tables will be prepared at each postdose time point and at the time of final IMP administration compared with baseline.

The numbers and percentages of subjects who have a visit with serum total bilirubin value of  $\geq 2$  times the upper limit of normal (ULN), and an aspartate aminotransferase (AST) or alanine aminotransferase (ALT) value of  $\geq 3$  times the ULN at any postdose time point will be calculated.

The numbers and percentages of subjects experiencing the following events after IMP administration will be calculated.

- A serum sodium concentration  $>147$  mEq/L
- A  $>10$  mEq/L increase in serum sodium concentration within 24 hours after the start of IMP administration

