3.4.3 Exclusion Criteria

Subjects will be excluded if they meet any of the exclusion criteria in [Table 3.4.3-1](#).

Table 3.4.3-1 Exclusion Criteria	
1	Patients who are on a ventricular assist device
2	Patients who have any of the following diseases, complications, or conditions: 
 • Suspected hypovolemia • Hypertrophic cardiomyopathy (excluding dilated phase) • Valvular disease with significant valvular stenosis • Hepatic encephalopathy with difficulty in adequate fluid intake
3	Patients who have experienced acute myocardial infarction within 30 days prior to the screening examination
4	Patients with a definite diagnosis of active myocarditis or amyloid cardiomyopathy
5	Patients who have any of the following medical histories: 
 • History of sustained ventricular tachycardia or ventricular fibrillation within 30 days prior to the screening examination (for patients without an implantable cardioverter defibrillator) • History of cerebrovascular disease (excluding asymptomatic cerebral infarction) within 6 months prior to the screening examination • History of hypersensitivity or idiosyncratic reaction to benzazepines or benzazepine derivatives such as the ingredients of OPC-61815, tolvaptan, mozavaptan hydrochloride, and benazepril hydrochloride
6	Patients who have any of the following diseases, complications, or conditions: 
 • Poorly controlled diabetes mellitus • Anuria • Dysuria associated with urinary tract obstruction, calculus, or tumor
7	Patients with supine systolic blood pressure of <90 mmHg
8	Patients with any of the following abnormalities in laboratory test results: 
 • Total bilirubin: >3.0 mg/dL • Serum or plasma creatinine: >3.0 mg/dL • Serum or plasma sodium concentration: <125 mEq/L

Table 3.4.3-1 Exclusion Criteria

	
 • Serum or plasma sodium concentration: >147 mEq/L • Serum or plasma potassium concentration: >5.5 mEq/L
9	Patients with current symptoms or a history of hepatic impairment (including patients with aspartate aminotransferase [AST] or alanine aminotransferase [ALT] exceeding 3 times the upper limit of the reference range at the screening examination)
10	Patients who have undergone open-heart surgery (eg, open-heart surgery for valvular disease, coronary bypass surgery, or surgery in thoracic aorta) within 30 days prior to the screening examination

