- Pregnancies are also defined as IREs. Although normal pregnancy is not an AE, it will mandate IMP discontinuation and must be reported on an IRE form to the sponsor. Pregnancy will only be documented on the AE eCRF if there is an abnormality or complication. The above applies to pregnancies of both subjects and their partners.

Clinical Laboratory Test Value Changes: It is the investigator or subinvestigator's responsibility to review the results of all laboratory tests as they become available. This review will be documented by the investigator or subinvestigator's dated signature on the laboratory report. For each abnormal laboratory test result, the investigator needs to ascertain if this is an abnormal (ie, clinically significant) change from baseline for that individual subject. This determination, however, does not necessarily need to be made the first time an abnormal value is observed. The investigator or subinvestigator may repeat the laboratory test or request additional tests to verify the results of the original laboratory tests. If this laboratory value is considered medically relevant by the investigator or subinvestigator (subject is symptomatic, requiring corrective treatment or further evaluation), or if the laboratory value leads to discontinuation, and/or fulfills a seriousness criterion, this is considered an AE.

Severity: Adverse events will be graded on a 3-point scale. The intensity of an adverse experience is defined as follows:

- 1 = Mild:** Discomfort noticed, but no disruption to daily activity.
- 2 = Moderate:** Discomfort sufficient to reduce or affect normal daily activity.
- 3 = Severe:** Inability to work or perform normal daily activity.

IMP Causality: Assessment of causal relationship of an AE to the use of the IMP is defined as follows:

- Related:** There is a reasonable possibility of a temporal and causal relationship between the IMP and the AE.
- Not Related:** There is no temporal or causal relationship between the IMP and the AE.

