7.4.1.2 Clinical Laboratory Data

Clinical laboratory data obtained from central measurements will be used for analyses. For clinical laboratory test parameters other than qualitative urinalysis, measured values and changes from baseline at each time point and at the time of final IMP administration will be summarized using descriptive statistics (the number of subjects, mean, SD, minimum, median, and maximum). For qualitative urinalysis parameters, shift tables will be prepared at each time point and at the time of final IMP administration compared with baseline. In addition, measured values of clinical laboratory test parameters other than qualitative urinalysis will be categorized as below, within, or above the normal range, and shift tables will be prepared at each postdose time point and at the time of final IMP administration compared with baseline.

The numbers and percentages of subjects who have a visit with serum total bilirubin value of ≥ 2 times the ULN, and an AST or ALT value of ≥ 3 times the ULN at any postdose time point will be calculated.

The numbers and percentages of subjects experiencing the following events after IMP administration will be calculated.

- A serum sodium concentration >147 mEq/L
- A >10 mEq/L increase in serum sodium concentration within 24 hours after the start of IMP administration

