### **3.4 Handling of Time Points**

Case report form (CRF) Visit values at each time point (time points from baseline in the screening, treatment, and follow-up periods as specified in the protocol Table 3.7.1) will be used in summaries (but values at the time of discontinuation will not be used in summaries). Unscheduled Visit values will not be used.

According to the rules specified in the protocol [Section 3.2.3](#), for the completion assessment of subjects who have completed treatment after a treatment period of shorter than 5 days, the CRF Visit will be set to correspond with the day of assessment for the analysis visit. Concerning interval urine samples, the daily urine volume will be calculated by summing all the interval urine volumes that constitute the daily urine volume for that day. If the interval urine sample is the last one for that day, the corresponding interval will be set as the analysis interval. The same rules also apply to fluid intake and urine electrolyte excretion. Other variables specified in the corresponding CRF Visit to be measured multiple times will be set to precede IMP administration.

Baseline and final administration time point for each variable are defined as follows.

Table 3.4-1 Handling of Time Points		
Variable	Baseline	Final Administration Time Point
Clinical laboratory value	Before IMP administration on Day 1	Day after final IMP administration
Vital signs	Before IMP administration on Day 1 (Screening values will be used if the values at screening are measured on Day 1 but not measured prior to the IMP administration on that day.)	Day after final IMP administration
12-lead ECG	Before IMP administration on Day 1	Day after final IMP administration
Daily urine volume, daily fluid intake, daily fluid balance	Within 24 hours before IMP administration on Day 1	-
Serum sodium concentration, serum potassium concentration, serum osmolality	Before IMP administration on Day 1	-
Daily urine sodium excretion, daily urine potassium excretion	Within 24 hours before IMP administration on Day 1	-
Urine osmolality	Within 24 hours before IMP administration on Day 1	-
Biomarkers (plasma AVP concentration, plasma renin activity, plasma brain natriuretic peptide [BNP] concentration, serum N-terminal pro-brain natriuretic peptide [NT-proBNP] concentration, and serum troponin I concentration)	Before IMP administration on Day 1	Day after final IMP administration

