### 7.3 Baseline Disease Evaluation

For the safety analysis set and efficacy analysis set, each variable at baseline will be calculated.

Table 7.3-1 Baseline Pathologic Evaluation		
Variable	Method	Level
Cardiothoracic ratio (%)	Descriptive statistics	-
NYHA classification	Distribution	Class I, Class II, Class III, Class IV
Severity of lower limb edema	Distribution	None, Mild, Moderate, Severe
Pulmonary congestion	Distribution	None, Mild, Moderate, Severe
Presence of jugular venous distension	Distribution	Yes, No
Jugular venous distension (cm)	Descriptive statistics	-
Presence of jugular venous distension (value at baseline)	Distribution	Yes, No
Jugular venous distension (cm) (subjects with baseline value)	Descriptive statistics	-
Presence of hepatomegaly	Distribution	Yes, No
Hepatomegaly (cm)	Descriptive statistics	-
Presence of hepatomegaly (value at baseline)	Distribution	Yes, No
Hepatomegaly (cm) (subjects with baseline value)	Descriptive statistics	-
Pulmonary rales	Distribution	Yes, No
Third cardiac sound	Distribution	Yes, No
Respiratory rate (breaths/min)	Descriptive statistics	-
Orthopnea	Distribution	Present, Absent
Paroxysmal nocturnal dyspnea	Distribution	Present, Absent
Subject-assessed dyspnea (presence of symptoms)	Distribution	Present, Absent
Daily urine volume	Distribution	<1500 mL, ≥1500 mL
Creatinine	Distribution	<2 mg/dL, ≥2 mg/dL
Plasma AVP concentration	Distribution	≤3.1 pg/mL, >3.1 pg/mL

Table 7.3-1 Baseline Pathologic Evaluation		
Variable	Method	Level
Albumin	Distribution	<3 g/dL, ≥3 g/dL

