### **9.6 Electrocardiogram Data**

For 12-lead ECG parameters, measured values and changes from baseline will be summarized at each time point and at the time of final IMP administration using descriptive statistics.

The numbers and percentages of subjects who have a QT corrected for heart rate (QTc) interval of >450, >480, or >500 msec at any postdose time point until the time of final IMP administration will be calculated. The numbers and percentages of subjects who have a change in QTc interval from baseline of >30 and >60 msec at any postdose time point or at the time of final IMP administration will be calculated. Also at baseline and at each postdose time point, the numbers and percentages of subjects will be calculated in the same manner as described above.

A shift table showing interpretation (normal or abnormal) will be prepared at each postdose time point and at the time of final IMP administration compared to baseline. Interpretation (normal or abnormal) assessments by the trial site (investigator or subinvestigator) will be used.

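### No table counts subjects by creatinine rise from their own baseline, and the normal-range shift table cannot register a further rise in a subject already above normal at entry

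*SAP*

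**What the plan says.** SAP 9.3 and Protocol 7.4.1.2 treat creatinine like every other quantitative laboratory test. Values and changes from baseline are summarised by "the number of subjects, mean, SD, minimum, median, and maximum". In addition, "measured values of clinical laboratory test parameters other than qualitative urinalysis will be categorized as below, within, or above the normal range", with shift tables against baseline. In SAP Appendix 1 these become CT-10.1.1 and CT-10.3.1, with listings CT-10.4.1 and LAB-1.

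The entry limit in Protocol 3.4.3 is "Serum or plasma creatinine: >3.0 mg/dL", so lower values are admitted. SAP Table 7.3-1 tabulates baseline creatinine as "<2 mg/dL, ≥2 mg/dL", and Table 7.2-1 records renal impairment as a baseline complication. The plan therefore provides for subjects who enter with clearly raised values.

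Subject counts against a threshold are planned for three other measures:

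- liver tests (CT-10.5);
- sodium, above 147 mEq/L or rising by more than 10 mEq/L within 24 hours of a dose (CT-10.6);
- QTc, including a "change in QTc interval from baseline of >30 and >60 msec at any postdose time point" (SAP 9.6).

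Creatinine has no equivalent. Its other route into the tables is the adverse-event count. Protocol 5.1 asks the investigator, for each abnormal result, to "ascertain if this is an abnormal (ie, clinically significant) change from baseline for that individual subject", and gives no numeric rule for creatinine.

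**The concern.** A three-level shift table records only a crossing of a normal limit. A subject above normal at entry has no higher category to move into, so worsening leaves no trace there, while a trivial move across the limit is recorded. The descriptive rows give the size of the largest change but not the number of subjects with a change of a given size.

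Tolerability is the trial's only objective. The population cannot correct fluid balance by drinking, and loop diuretics continue throughout treatment. Protocol 1.3 lists raised creatinine and renal impairment among the frequent tolvaptan events. Protocol 1.2.2 reports raised creatinine in 2 of 48 phase 2 subjects on OPC-61815 (4.2%), and renal impairment among the reasons for stopping treatment. Without a fixed-definition count, a reader must rely on events judged case by case at about 25 open-label sites, or count by hand from the listings.

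**Working it through.** **Plan's own figure.** The plan has no figure for creatinine. Its one safety calculation is the chance of seeing at least one event in 40 subjects: 1 − 0.95^40 = 0.871 and 1 − 0.96^40 = 0.805. These match the stated 87% and 80%, and this point does not affect them.

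**Shift table.** The documents do not give the upper limit of normal (ULN). Assume 1.1 mg/dL; any limit from 1.0 up to, but not including, 1.15 gives the same four readings.

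- 1.5 to 2.5 (+1.0, 1.67 times): above to above
- 2.0 to 3.0 (+1.0, 1.50 times): above to above
- 2.9 to 4.4 (+1.5, 1.52 times): above to above
- 1.0 to 1.15 (+0.15, 1.15 times): within to above

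The three large rises show as no shift, and the trivial one shows as a shift.

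**How many rises could sit there.** Assume 10% of 40 subjects have a true rise (4 expected), independent of baseline status. If 30%, 50% or 70% enter above normal, the expected number of rises in the above-to-above cell is 4 × 0.3 = 1.2, 4 × 0.5 = 2.0 or 4 × 0.7 = 2.8. The documents do not give the share above normal at entry.

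**Mean change.** Four subjects at +1.0 and 36 at −0.1 mg/dL give (4.0 − 3.6)/40 = +0.01 mg/dL. The maximum row would show +1.0, but not that four subjects had it.

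**Constructed example.** There are 40 subjects, with one postdose time point, overall rows only, and a ULN assumed above 1.0 and below 1.5 mg/dL. In both cases 31 subjects go from 1.0 to 0.95.

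- Case A adds three each of 1.5 to 1.9, 1.9 to 2.7, and 2.3 to 2.3.
- Case B adds three each of 1.5 to 2.3, 1.9 to 1.9, and 2.3 to 2.7.

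| Row (mg/dL), same in A and B | Mean | SD | Min | Median | Max |
|---|---|---|---|---|---|
| Baseline | 1.20 | 0.41 | 1.0 | 1.0 | 2.3 |
| Postdose | 1.25 | 0.59 | 0.95 | 0.95 | 2.7 |
| Change | +0.05 | 0.25 | −0.05 | −0.05 | +0.8 |

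The shift table is also the same: 31 within to within and 9 above to above. The counts that could be added are:

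| Definition of rise | Case A | Case B |
|---|---|---|
| ≥0.3 mg/dL | 6 | 6 |
| ≥0.5 mg/dL | 3 | 3 |
| ≥1.25 times | 6 | 3 |
| ≥1.4 times | 3 | 3 |
| ≥1.5 times | 0 | 3 |
| ≥2 times | 0 | 0 |

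The ratios behind the last four rows, for the subjects whose creatinine rises, are 1.267 and 1.421 in A, and 1.533 and 1.174 in B. The absolute counts agree because both cases contain the same set of changes: three at +0.8, three at +0.4, three at 0 and 31 at −0.05.

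**Precision (Clopper-Pearson 95%).** 0/40: 0% to 8.8%. 3/40 = 7.5%: 1.6% to 20.4%. 6/40 = 15%: 5.7% to 29.8%.

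**The case against.** The strongest reply is that creatinine is already well covered. Change is summarised with its maximum, abnormal values are listed, and renal events are counted by preferred term, severity, seriousness, relatedness and discontinuation. The event route picked up renal signals in phase 2. With 40 subjects and two scheduled postdose panels, anyone can count from LAB-1. Sodium and the transaminases get special counts because the protocol sets on-treatment action limits for them and names hypernatremia, dehydration and thirst as this population's added risks. It sets no such limit for creatinine. All of this stands, and it limits the weight of the point. It does not supply a count on a fixed definition.

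Three stronger readings are tempting, and the documents do not support them.

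- A reader might infer from Cases A and B that the planned output as a whole cannot separate 0% from 7.5%. The example covers only overall rows at one postdose time point. SAP 9 repeats the analyses by dose-escalation group and SAP 9.3 covers each time point, so the match would also need balance there. The contrast also exists only at 1.5 times baseline. At 1.25 times it reverses, and on any absolute rise it disappears.
- A reader might infer that a multiple of baseline is the natural main cut-off. It is least sensitive in the subjects at issue: a subject entering at 2.0 mg/dL must rise by 1.0 to reach 1.5 times. In Case A, six subjects above normal at entry rise by 0.4 or 0.8, and a 1.5-times row reports 0 of 40.
- SAP 3.4 says that "values at the time of discontinuation will not be used in summaries", from which a reader might infer that withdrawal creatinine is lost. Table 3.4-1 defines the laboratory final-administration point as "Day after final IMP administration", and SAP 5.4 fills gaps with the last value up to that day. That sample therefore already enters the final-administration rows.

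**Conclusion.** The gap is real and of modest weight. It is a cheap improvement to a safety table, not an analysis error, and renal change is not left unanalysed. The summary tables will show that creatinine rose in someone and by how much at most. They will not show in how many subjects it rose by a stated amount, and the shift table cannot show worsening in subjects who enter above normal.

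That conclusion rests on the text alone. The sizes rest on assumptions: a ULN not given in the documents, an assumed 30% to 70% above normal at entry, and constructed values. The example shows only that the overall rows at one time point do not determine a ratio-based count. It does not predict what the trial will find.

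**What to change.** In SAP 9.3, beside CT-10.6, add the number and percentage of subjects, overall and by the planned dose-escalation grouping, whose central creatinine at any postdose sample exceeds the Day 1 predose value by prespecified absolute amounts, for example at least 0.3 and at least 0.5 mg/dL. This follows the absolute-rise counts already planned for sodium and QTc, and it can register rises in subjects with a raised baseline. Add at least 1.5 times and at least 2 times baseline as supplementary rows. Define the postdose samples as the day after the final dose, including the withdrawal assessment, and follow-up. In view of SAP 3.4, state explicitly that the withdrawal sample counts.

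The cost is a few rows in one table. The central panels at Day 1 predose, Day 6 or withdrawal, and follow-up are already scheduled, so no new sample or visit is needed. The limits should be stated with the table. The cut-offs are conventional and not taken from the documents. Counts will be small, with wide intervals. Without a control arm they describe and do not attribute. Transient rises between Day 1 and Day 6 will still be missed, because no central laboratory panel is scheduled between them.

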### **9.4 Vital Sign Data**

For vital signs (blood pressure, pulse rate, and body temperature), measured values and changes from baseline at each time point and at the time of final IMP administration will be summarized using descriptive statistics.

### **9.5 Physical Examination Data**

No physical examination data analysis will be performed in this trial.

### **9.6 Electrocardiogram Data**

For 12-lead ECG parameters, measured values and changes from baseline will be summarized at each time point and at the time of final IMP administration using descriptive statistics.

The numbers and percentages of subjects who have a QT corrected for heart rate (QTc) interval of >450, >480, or >500 msec at any postdose time point until the time of final IMP administration will be calculated. The numbers and percentages of subjects who have a change in QTc interval from baseline of >30 and >60 msec at any postdose time point or at the time of final IMP administration will be calculated. Also at baseline and at each postdose time point, the numbers and percentages of subjects will be calculated in the same manner as described above.

A shift table showing interpretation (normal or abnormal) will be prepared at each postdose time point and at the time of final IMP administration compared to baseline. Interpretation (normal or abnormal) assessments by the trial site (investigator or subinvestigator) will be used.

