3.7.1 Schedule of Assessments

3.7.1.1 Screening Period (Day -1 to Predose on Day 1)

3.7.1.1.1 Screening Examination

Between Day -1 and predose on Day 1, the investigator or subinvestigator will obtain consent from the subject, and then conduct the following examinations and tests to assess the eligibility of the subject for participation in the trial.

[Examinations and tests]

- Subject background
(Birth date, sex, height, country, race, ethnicity, underlying disease, type of heart failure, presence and type of arrhythmias, presence of a pacemaker, presence of an implantable cardioverter defibrillator, complications, medical history, and reason(s) why oral intake is considered to be difficult or impossible)
- Serum sodium concentration (local measurement)
- Serum potassium concentration (local measurement)
- Body weight
- Dyspnea (respiratory rate, paroxysmal nocturnal dyspnea, orthopnea, and subject-assessed dyspnea [assessment of the presence of the symptoms by the subject])
- Congestive symptoms (lower limb edema, hepatomegaly, jugular venous distension, pulmonary rales, and cardiac third sound)
- Chest x-ray (cardiothoracic ratio and pulmonary congestion)
Chest x-ray does not have to be repeated if it has been performed within 24 hours before informed consent. The results of chest x-ray performed prior to the acquisition of informed consent can be used to determine the eligibility of the subject to participate in the trial.
- Clinical laboratory tests (local measurement)
- Physical examination
- Vital signs (blood pressure, pulse rate, and body temperature)
- NYHA classification
- Concomitant medications and therapies
- Urine pregnancy test (WOCBP only)

Date of informed consent, subject identifier, the result of eligibility assessment, and subject characteristics will be recorded in the eCRF. Subjects must be hospitalized from the time of informed consent through the completion (withdrawal) assessment.

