## **5 Statistical Analysis Datasets**

### **5.1 Safety Analysis Set**

The safety dataset includes all subjects who received at least one dose of IMP.

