- CT-10.1.3 Mean Change from Baseline in Clinical Laboratory Test Results (Urinalysis) (Safety Analysis Set)
- CT-10.2 Shift Tables of Clinical Laboratory Test Results (Qualitative Urinalysis) (Safety Analysis Set)
- CT-10.3.1 Shift Tables of Clinical Laboratory Test Results (Serum Chemistry) (Safety Analysis Set)
- CT-10.3.2 Shift Tables of Clinical Laboratory Test Results (NA, K) (Safety Analysis Set)
- CT-10.3.3 Shift Tables of Clinical Laboratory Test Results (Hematology) (Safety Analysis Set)
- CT-10.3.4 Shift Tables of Clinical Laboratory Test Results (Urinalysis) (Safety Analysis Set)
- CT-10.4.1 Listing of Abnormal Laboratory Findings (IMP Administered Subjects)
- CT-10.4.2 Listing of Abnormal Laboratory Findings Potential Drug-Induced Liver Injury (IMP Administered Subjects)
- CT-10.5 Incidence of Potential Drug-Induced Liver Injury (Safety Analysis Set)
- CT-10.6 Incidence of Sodium Related Events (Safety Analysis Set)
- CT-11 Mean Change from Baseline in Vital Signs (Safety Analysis Set)
- CT-12.1 Mean Change from Baseline in Electrocardiogram Results (Safety Analysis Set)
- CT-12.2.1 Shift Table of 12-Lead ECG Findings (Normal/Abnormal Assessments) (Safety Analysis Set)
- CT-12.3.1 Incidence of Categorical Changes in Electrocardiogram Results (Post baseline any visit) (Safety Analysis Set)
- CT-12.3.2 Incidence of Categorical Changes in Electrocardiogram Results (Each Visit) (Safety Analysis Set)
- PDT-1.1 Descriptive Statistics for Daily Urine Volume (mL) (Pharmacodynamic Analysis Set)
- PDT-1.2.1 Descriptive Statistics for Interval Urine Volume (mL) (Pharmacodynamic Analysis Set)

PDT-1.2.2 Descriptive Statistics for Interval Urine Volume (mL) by Dose Escalation (Pharmacodynamic Analysis Set)

PDT-1.3.1 Descriptive Statistics for Cumulative Urine Volume (mL) (Pharmacodynamic Analysis Set)

PDT-1.3.2 Descriptive Statistics for Cumulative Urine Volume (mL) by Dose Escalation (Pharmacodynamic Analysis Set)

PDT-2.1 Descriptive Statistics for Daily Fluid Intake (mL) (Pharmacodynamic Analysis Set)

PDT-2.2.1 Descriptive Statistics for Interval Fluid Intake (mL) (Pharmacodynamic Analysis Set)

PDT-2.2.2 Descriptive Statistics for Interval Fluid Intake (mL) by Dose Escalation (Pharmacodynamic Analysis Set)

PDT-2.3.1 Descriptive Statistics for Cumulative Fluid Intake (mL) (Pharmacodynamic Analysis Set)

PDT-2.3.2 Descriptive Statistics for Cumulative Fluid Intake (mL) by Dose Escalation (Pharmacodynamic Analysis Set)

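### The any-postdose QTc counts in SAP 9.6 ignore the predose value, so the summary tables do not show how many subjects newly crossed 450, 480 or 500 msec

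*SAP*

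**What the plan says.** SAP 9.6, like protocol 7.4.1.4, plans these categorical ECG summaries:

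- **Absolute limits.** Subjects with QTc above 450, 480 or 500 "msec at any postdose time point until the time of final IMP administration will be calculated". Nothing is required of the baseline value. The output is CT-12.3.1, "Incidence of Categorical Changes in Electrocardiogram Results (Post baseline any visit) (Safety Analysis Set", and the population is every treated subject: "The safety dataset includes all subjects who received at least one dose of IMP" (SAP 5.1).
- **Change from baseline.** Subjects with a "change in QTc interval from baseline of >30 and >60 msec at any postdose time point or at the time of final IMP administration".
- **Baseline and visit counts.** "Also at baseline and at each postdose time point, the numbers and percentages of subjects will be calculated in the same manner as described above" (CT-12.3.2).
- **Shift table.** "A shift table showing interpretation (normal or abnormal) will be prepared at each postdose time point", using the site's assessment (CT-12.2.1). Protocol 7.4.1.4 describes this table as one of QTc interpretation; the SAP text no longer names QTc.

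The ECG baseline in SAP Table 3.4-1 is "Before IMP administration on Day 1". Appendix 2 of the SAP plans by-subject ECG listings from the central laboratory (PDATA-6.1) and the trial site (PDATA-6.2).

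The exclusion criteria in protocol Table 3.4.3-1 set limits on blood pressure, bilirubin, creatinine, sodium, potassium and AST/ALT. None sets a QTc limit; only the general discretion in criterion 15 could act. The screening examination includes no ECG, but it records "presence and type of arrhythmias, presence of a pacemaker, presence of an implantable cardioverter defibrillator".

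**The concern.** A count of subjects above a QTc limit after dosing is easily read as a count of subjects who went above it after dosing. Here the two can differ, because entry is open to subjects who are already above a limit. The title of CT-12.3.1, which speaks of incidence and of change, encourages the first reading.

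The trial is meant to confirm tolerability and has no control arm, so each subject's own predose ECG is the only reference. SAP section 9 also repeats the safety analyses for subjects with and without escalation to 16 mg. Those groups are not randomised, so a difference in baseline QTc between them would carry into the any-postdose counts and could look related to dose.

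Elsewhere the SAP does condition on baseline: the resolution rates in 8.3.2.1, 8.3.2.3 and 8.3.3.2 cover only subjects who had the symptom at baseline.

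**Working it through.** The plan states no figure for QTc. Its only design figure, the chance of seeing at least one event in 40 subjects, reproduces: 1 − 0.95^40 = 0.871 (stated 87%) and 1 − 0.96^40 = 0.805 (stated 80%). It does not bear on this point, which is one of definition.

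**1. Do the separate counts give the new-onset number?** Let B be the number above a limit at baseline and P the number above it at any postdose time point, out of n. Among the P, the subjects who were at or below the limit at baseline number at least max(0, P − B) and at most min(P, n − B). Take hypothetical values B = 8, P = 10, n = 40:

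- minimum: max(0, 10 − 8) = 2
- maximum: min(10, 40 − 8) = 10

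The per-visit postdose totals do not narrow this, because they do not say which subjects were above the limit at baseline.

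**2. Do the change counts fill the gap?** Not by themselves. These are constructed examples.

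| Predose to postdose QTc (msec) | Change | Newly above | Counted as >30 | Counted as >60 |
|---|---|---|---|---|
| 490 to 505 | +15 | 500 | no | no |
| 455 to 499 | +44 | 480 | yes | no |
| 505 to 560 | +55 | none | yes | no |

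The first row is a new crossing that the change counts miss. The third is a worsening that a new-onset count misses. Each type of count shows something that the other does not.

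**3. Does the shift table fill it?** No. It has two categories, normal and abnormal, for the ECG as a whole. It cannot show movement across 450, 480 or 500 msec.

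**4. How far could the planned count and the new-onset count differ?** The documents do not give the inputs, so this shows the mechanism only and is not an estimate. Let b be the share above a limit at baseline, r the share of those still above it at some postdose ECG, and q the new-onset rate among the rest. Then

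planned count = 40·b·r + 40·(1 − b)·q.

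With r = 0.9 and q = 5%, both assumed:

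| b (assumed) | Already above | New | Planned count | Share already above | New-onset rate |
|---|---|---|---|---|---|
| 0% | 0 | 2.0 | 2.0/40 | 0% | 2.0/40 = 5% |
| 5% | 1.8 | 1.9 | 3.7/40 | 49% | 1.9/38 = 5% |
| 10% | 3.6 | 1.8 | 5.4/40 | 67% | 1.8/36 = 5% |
| 20% | 7.2 | 1.6 | 8.8/40 | 82% | 1.6/32 = 5% |
| 50% | 18.0 | 1.0 | 19.0/40 | 95% | 1.0/20 = 5% |

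At b = 20% the share already above runs from 64% (r = 0.7, q = 10%) to 83% (r = 1, q = 5%). If nobody starts above a limit, the two counts are the same.

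**The case against.** The strongest reply is that SAP 9.6 does not rest on the absolute counts alone. It also plans changes from baseline at each time point, counts of increases over 30 and 60 msec, and the threshold counts at baseline. The change counts are a within-subject analysis: a subject who sits at the same high value before and after dosing adds nothing to them. The statistic is also described accurately, since SAP 9.6 does not call these subjects new-onset or drug-related. All of this stands.

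It also rules out some stronger readings that a reader might infer:

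- **That nothing in the plan separates pre-existing prolongation from change on treatment.** The change counts and the baseline counts contradict this.
- **That a new value above 500 msec could not be told from an old one.** The protocol schedules four ECGs per subject: Day 1 predose, 1 hour after the start of dosing on Day 1, Day 3, and Day 6 or withdrawal. For 40 subjects that is 4 × 40 = 160 scheduled records, and PDATA-6.1 and PDATA-6.2 list them by subject. Any case can be traced by hand; only the summary tables lack the cross-classification.
- **That every subject above a limit at baseline is counted.** Only those still above it at a postdose ECG are.
- **That many false cases should be expected.** The documents say which cardiac history items are recorded at screening, but not how common they are or what the QTc values will be.
- **That new-onset counts should replace the current ones.** That would take the change from 505 to 560 msec out of the absolute-limit results altogether.

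What remains is that none of these outputs tabulates how many subjects newly crossed each limit.

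**Conclusion.** The point holds as a minor gap in presentation. The any-postdose counts at 450, 480 and 500 msec combine subjects who were already above a limit with subjects who crossed it after dosing, and no planned summary table separates them. The baseline data exist and are reported, but as totals that are not linked to the postdose categories.

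This conclusion rests on the text of SAP 9.6, the SAP list of tables and the exclusion criteria, and needs no assumption about QTc values. Its size does need one: the effect could be nil if no subject starts above a limit, and the illustrative prevalences above carry no evidential weight. The lack of a control arm makes the within-subject result more useful here than it would be in a randomised trial.

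**What to change.** Keep the all-subject counts and the counts of increases over 30 and 60 msec as they are. Add one of the following to SAP 9.6 and CT-12.3.1:

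- for each limit, the number of subjects with Day 1 predose QTc at or below it and any postdose value above it, with subjects at or below the limit at baseline as denominator; or
- a shift table of baseline QTc category by worst postdose QTc category, with categories ≤450, >450–480, >480–500 and >500 msec.

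Use the baseline in SAP Table 3.4-1 and the same visit rules as for the existing counts. Report the addition alongside those counts, not in place of them, so that worsening in subjects already above a limit stays visible.

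The cost is a short change to the SAP wording and a few table rows. No new ECG, visit or data item is needed. The drawback is that the new-onset rates have smaller denominators, and so are less precise, than rates over the whole safety set.
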